5.9 Criteria for Taking a Participant Off Protocol Therapy

The following are criteria for removing a participant from active study:

- The development of steroid-requiring cGVHD
- Malignant disease progression
- Intercurrent illness that prevents further administration of treatment
- Unacceptable adverse event(s)
- Participant demonstrates an inability or unwillingness to comply with the treatment regimen
- Participant decides to withdraw from the protocol therapy
- General or specific changes in the participant's condition render the participant unacceptable for further treatment in the judgment of the treating investigator

Participants will be removed from the protocol therapy when any of these criteria apply. The reason for removal from protocol therapy, and the date the participant was removed, must be documented in the case report form (CRF). Patients with steroid-requiring cGVHD, unacceptable AEs or intercurrent illness preventing further drug administration who come off treatment should continue to have laboratory studies and clinical assessments performed at the appropriate timepoints. Patients with malignant disease progression do not require laboratory or clinical follow-up. Alternative care options will be discussed with the participant.

An ODQ/CTRIO Treatment Ended/Off Study Form will be filled out when a participant is removed from protocol therapy. This form can be found on the ODQ/CTRIO website or obtained from the ODQ/CTRIO registration staff.

In the event of unusual or life-threatening complications, treating investigators must immediately notify the Overall PI, [name] at [contact] [name].

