5.10 Duration of Follow Up

Research subjects will be followed until 2 years from the time of transplantation, or until death, whichever occurs first. Participants removed from protocol therapy for unacceptable adverse events will be followed closely until resolution or stabilization of the adverse event, and then until 2 years from the time of transplantation, or until death, whichever occurs first. Participants who withdraw consent will be followed until that time.

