7.3 Expedited Adverse Event Reporting

- 7.3.1 Investigators **must** report to the Overall PI any serious adverse event (SAE) that occurs after the initial dose of study treatment, during treatment, or within 30 days of the last dose of treatment on the local institutional SAE form.
- 7.3.2 For multi-institution studies where a DF/HCC investigator is serving as the Overall Principal Investigator, each participating institution **must** abide by the reporting requirements set by the DF/HCC. This applies to any medical event equivalent to an unexpected grade 2 or 3 with a possible, probable or definite attribution, unexpected grade 4 toxicities, and grade 5 (death) regardless of study phase or attribution.

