7.3.3 DF/HCC Expedited Reporting Guidelines

Investigative sites within DF/HCC will report AEs directly to the DFCI Office for Human Research Studies (OHRS) per the DFCI IRB reporting policy.

Other investigative sites will report AEs to their respective IRB according to the local IRB's policies and procedures in reporting adverse events. A copy of the submitted institutional AE form should be forwarded to the Overall PI within the timeframes detailed in the table below.

	DF/HCC Reportable AEs									
Attribution	Gr. 2 & 3 AE Expected	Gr. 2 & 3 AE Unexpected	Gr. 4 AE Expected	Gr. 4 AE Unexpected	Gr. 5 AE Expected or Unexpected					
Unrelated Unlikely	Not required	Not required	5 calendar days#	5 calendar days	24 hours*					
Possible Probable Definite	Not required	5 calendar days	5 calendar days#	5 calendar days	24 hours*					

[#] If listed in protocol as expected and not requiring expedited reporting, event does not need to be reported.

The Overall PI will submit AE reports from outside institutions to the DFCI OHRS according to DFCI IRB policies and procedures in reporting adverse events.

7.3.4 Protocol-Specific Expedited Adverse Event Reporting Exclusions

For this protocol only, the AEs/grades listed below do not require expedited reporting to the Overall PI or the DFCI IRB. However, they still must be reported through the routine reporting mechanism (i.e. case report form).

The appearance of signs or symptoms known to be associated with acute or chronic GVHD are specifically exempt from AE or SAE reporting, regardless of their severity.

^{*} For participants enrolled and actively participating in the study *or* for AEs occurring within 30 days of the last intervention, the AE should be reported within 1 business day of learning of the event.

Similarly, infectious complications following stem cell transplantation are common, and will not be reported as AEs unless the clinical investigator deems the infection to be very atypical for the post-transplant setting, or the infection results in death.

Relapse of the original malignancy will not be reported as an AE, but will be monitored, as detailed in section 12.7

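### Section 7.3.4 contradicts itself on whether ordinary non-fatal infections go on the case report form, and 12.5 compares infections by arm only when they are judged treatment-related

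*Combined protocol and SAP*

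**What the plan says.** **Recording.** The lead-in to 7.3.4 removes expedited reporting to the Overall PI and the IRB for the events listed under it, but adds that "they still must be reported through the routine reporting mechanism (i.e. case report form". Three items follow. GVHD signs and symptoms are "specifically exempt from AE or SAE reporting, regardless of their severity". Infections "will not be reported as AEs unless the clinical investigator deems the infection to be very atypical for the post-transplant setting", with fatal infections as the other exception. Relapse is not an AE but is monitored under 12.7.

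**Other routes.** 7.3.1 requires SAE reports to the Overall PI after the first dose, during treatment, "or within 30 days of the last dose of treatment on the local institutional SAE form". 7.3.2 covers unexpected grade 2-3 events with at least possible attribution, unexpected grade 4 events, and deaths. 7.4.6 covers SAEs after study participation if attributed to study drug. 7.5 permits, but does not oblige, sites to report serious infection as an event of special interest. 7.6 requires SAE reports to the manufacturer and gives a timeline only for related ones.

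**Follow-up.** 5.10 states: "Research subjects will be followed until 2 years from the time of transplantation, or until death, whichever occurs first". Under 5.9, one reason for stopping protocol therapy is "The development of steroid-requiring cGVHD". Those subjects, and those stopping for adverse events or intercurrent illness, "should continue to have laboratory studies and clinical assessments performed at the appropriate timepoints". By contrast, "Patients with malignant disease progression do not require laboratory or clinical follow-up".

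**Analysis and monitoring.** Infections are a secondary objective in 1.3, 12.1 and 12.7, with no attribution filter, and 7.1.3 lists them among AEs of particular interest. 12.7 states a method for hematologic events and none for infections. 12.5 compares three safety endpoints by arm: relapse, treatment-related toxicity of grade 3 or higher, and grade III-IV acute GVHD.

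**The concern.** The two statements in 7.3.4 cannot both be followed as written. A site that follows the infection sentence would record a non-fatal grade 3-4 infection only if its investigator found it very atypical. After transplantation that is a matter of opinion and will differ between centers. A named safety endpoint of a B-cell-depleting agent would then rest on discretionary reporting.

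The interim plan does not compensate. Infection enters the 12.5 comparison only through a judgement that it was caused by treatment, and the DSMB cannot review events that were never recorded. Infections that are not recorded prospectively may be hard to recover later.

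**Working it through.** The plan gives no figure for infections to reproduce. The 12.2 rates used in step 3 do reproduce the stated primary power: Fisher's exact test, 100 per arm, 38% vs 21%, two-sided 0.1 gives 80.8% against the stated 80%.

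**1. The three items of 7.3.4 side by side.**

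| Item | Exempt from | Where the text says it is captured instead |
|---|---|---|
| GVHD | AE and SAE reporting | Provider survey, Appendix F, months 6 to 24 |
| Relapse | AE reporting | Monitoring under 12.7 |
| Infection | AE reporting unless very atypical or fatal | Nothing named beyond the lead-in's general statement |

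The only infection row in the study calendar is pre-transplant testing. Because infections are exempted from AE reporting and GVHD from AE or SAE reporting, the status of a serious infection under 7.3.1 is also unclear.

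**2. What the 7.3.1 window covers.** Dose 1 is at day 90, the last dose at day 365 (5.3), and follow-up ends at about day 730 (5.10).
- All doses given: 365 + 30 = day 395. Uncovered: 730 − 395 = 335 of 730 − 90 = 640 days, or 52%.
- Dosing stopped after dose 1: 90 + 30 = day 120. Uncovered: 730 − 120 = 610 of 640 days, or 95%.

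**3. Does the window differ enough by arm to matter?** Let steroid-requiring cGVHD start at T = 3 + an exponential time, with hazard −ln(1 − p)/9 per month and p = 0.38 or 0.21 (12.2). The constant hazard is an assumption, and other reasons for stopping are ignored. The window closes at month 13 if T ≥ 12, otherwise at the later of T and last dose + 1 month. Its mean length is 7.84 months on placebo and 8.84 on obinutuzumab, out of 21.

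For an assumed 15% true infection rate in both arms, independent of cGVHD:

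| Infection hazard (assumed) | Share captured, placebo vs obinutuzumab | Difference per 100 subjects |
|---|---|---|
| Constant | 0.391 vs 0.440 | 15 × 0.049 = 0.74 |
| Halving every 6 months | 0.636 vs 0.698 | 15 × 0.062 = 0.93 |
| Halving every 3 months | 0.790 vs 0.849 | 15 × 0.059 = 0.89 |

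The difference is under one event per 100 in each case.

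**4. What incomplete recording could cost (illustration only).** Chi-square test, two-sided 0.05, 100 per arm. If 15% vs 30% were the true rates, power would be 73%, 54%, 40% and 24% at 100%, 70%, 50% and 30% capture. For 15% vs 25% it would be 43%, 30%, 22% and 14%. Every rate and capture fraction here is assumed. The one infection rate in the documents (15%, grade 3-5, 2 years; section 2.1) comes from rituximab-treated patients and is not a placebo estimate.

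**5. Effect of adding infection to 12.5.** Assume 15% in both arms, independent endpoints, and uniform accrual over 2 years. By simulation, one endpoint tested at 0.05 flags by chance in about 13.0% of trials over five looks and 16.0% over seven.
- Five looks: 1 − 0.870³ = 34% for three endpoints, 1 − 0.870⁴ = 43% for four.
- Seven looks: 1 − 0.840³ = 41%, 1 − 0.840⁴ = 50%.

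Power at a single look is low. Across true rates of 10% vs 20%, 15% vs 25% and 15% vs 30%, it is about 17% to 30% at 1.5 years and 27% to 48% at 2 years.

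**6. Why a cause-specific comparison is needed if relapse competes.** With constant hazards over 21 months, the cumulative incidence of infection is h_i/(h_i + h_r) × [1 − exp(−21(h_i + h_r))], where h_i and h_r are the infection and relapse hazards. For net infection of 15% vs 25% and relapse of 28% in both arms, it is 12.8% vs 21.5%, a gap of 8.6 points before rounding. If relapse were 40% in the second arm, it would be 12.8% vs 19.8%, a gap of 7.0 points. A relapse excess would hide part of an infection excess. The 28% is one of the two relapse figures in section 2.1; the 40% is assumed.

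**The case against.** The best defense is context. 7.3.4 sits under expedited reporting, and 7.2 describes its list in those terms. GVHD, the basis of the primary endpoint, is in the same list and plainly is collected, so exemption from AE reporting need not mean exemption from data collection. The case report forms are separate documents and may include an infection page. Toxicity assessments run to month 24, and Appendix D 3.9 says that all toxicities encountered are evaluated. This milder reading is possible, and it rules out any claim that infections will go unrecorded. It does not settle the matter, because the text points to another instrument for GVHD and relapse and to none for infections.

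A reader might infer three stronger things that the documents do not support:
- That unequal SAE windows bias the infection comparison between arms. Nothing in the protocol makes 7.3.1 forms the source of this endpoint, and step 3 puts the effect below one event per 100.
- That late serious infections depend on 7.6 alone. 7.3.2 states no end date and 7.4.6 covers later attributed SAEs. These routes are filtered, however, and do not add up to a full count by arm.
- That a known amount of power is lost. The capture fractions in step 4 have no source in the plan.

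On 12.5, the list is consultative, the DSMB may already receive events by category (11.2), and the study team judging attribution is blinded (12.3). Blinding limits bias between arms but does not make the count complete, and 11.2 does not promise an infection comparison by arm. Section 1.3 can be read as already applying cumulative incidence to infections, so the 12.7 point is mostly clarification.

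**Conclusion.** The contradiction in 7.3.4 is real and should be fixed. As written, a site may leave non-fatal grade 3-4 infections to investigator judgement, and no other route in the text gives a complete count by arm to month 24. "Grade 3-4" is used here for the events at stake; 7.3.4 itself names no grades for infection. Infection also lacks a by-arm interim comparison free of attribution, although 7.1.3 singles it out.

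The size of any loss is unknown, since it depends on site practice and on forms not in the documents. The power figures in step 4 show direction only. The difference between arms in 7.3.1 windows is minor under the assumptions in step 3. Because interim power is low even with full capture, the main gain is reliable final safety data rather than earlier warning.

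**What to change.** 1. **7.3.4.** Reword the infection sentence so that it exempts infections from expedited reporting only, and reconcile it with 7.3.1, 7.5 and 7.6. Record every grade 3-5 infection of any attribution on the case report form, with date and grade, from dose 1 to month 24 or the end of the subject's follow-up. Use the toxicity assessments already scheduled. Reconcile 5.9 with 5.10 and 5.11 on follow-up after progression; until that is done, capture after progression will be incomplete.
2. **12.5.** Add grade 3-5 infection of any attribution to the existing non-binding comparison by arm.
3. **12.7.** State cumulative incidence of first grade 3-5 infection with death as a competing event, and a cause-specific comparison alongside. Decide whether relapse also competes once the follow-up sections agree.

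**Cost.** A few case report form fields, one more row in a DSMB table, and no new visits. The downside is more chance consultations: from about 34% to 43% over five looks, or 41% to 50% over seven, under the assumptions in step 5. Overlap between endpoints would lower these figures, and none of the consultations is a stopping rule.

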7.4 Serious Adverse Events for Genentech Reporting

An AE should be classified as an SAE if the following criteria are met:

- It results in death (i.e., the AE actually causes or leads to death).
- It is life threatening (i.e., the AE, in the view of the investigator, places the patient at immediate risk of death. It does not include an AE that, had it occurred in a more severe form, might have caused death.).
- It requires or prolongs inpatient hospitalization.
- It results in persistent or significant disability/incapacity (i.e., the AE results in substantial disruption of the patient's ability to conduct normal life functions).
- It results in a congenital anomaly/birth defect in a neonate/infant born to a mother exposed to obinutuzumab.
- It is considered a significant medical event by the investigator based on medical judgment (e.g., may jeopardize the patient or may require medical/surgical intervention to prevent one of the outcomes listed above).

7.4.1 Deaths

All deaths that occur during the protocol-specified AE reporting period, regardless of attribution, will be reported to the appropriate parties. When recording a death, the event or condition that caused or contributed to the fatal outcome should be reported as the single medical concept. If the cause of death is unknown and cannot be ascertained at the time of reporting, report "Unexplained Death".

7.4.2 Preexisting Medical Conditions

A preexisting medical condition is one that is present at the start of the study. Such conditions should be reported as medical and surgical history. A preexisting medical condition should be re-assessed throughout the trial and reported as an AE or SAE only if the frequency, severity, or character of the condition worsens during the study. When reporting such events, it is important to convey the concept that the preexisting condition has changed by including applicable descriptors (e.g., "more frequent headaches").

7.4.3 Hospitalizations for Medical or Surgical Procedures

Any AE that results in hospitalization or prolonged hospitalization should be documented and reported as an SAE. If a patient is hospitalized to undergo a medical or surgical procedure as a result of an AE, the event responsible for the procedure, not the procedure itself, should be reported as the SAE. For example, if a patient is hospitalized to undergo coronary bypass surgery, record the heart condition that necessitated the bypass as the SAE.

Hospitalizations for the following reasons do not require reporting:

- Hospitalization or prolonged hospitalization for diagnostic or elective surgical procedures for preexisting conditions
- Hospitalization or prolonged hospitalization required to allow efficacy measurement for the study or
- Hospitalization or prolonged hospitalization for scheduled therapy of the target disease of the study.

7.4.4 Pregnancy

If a female patient becomes pregnant while receiving obinutuzumab or within one year after the last dose of obinutuzumab, or the partner of a male patient becomes pregnant while receiving therapy or within three months of completing therapy, a report should be completed and expeditiously submitted to the Roche/Genentech, Inc. Follow-up to obtain the outcome of the pregnancy should also occur. Abortion, whether accidental, therapeutic, or spontaneous, should always be classified as serious, and expeditiously reported as an SAE. Similarly, any congenital anomaly/birth defect in a child born to a female patient exposed to obinutuzumab should be reported as an SAE.

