3.1.11 The effects of obinutuzumab on the developing human fetus are unknown. For this reason, women of child-bearing potential and men must agree to use adequate contraception (hormonal or barrier method of birth control; abstinence) prior to study entry and for the duration of study participation. Should a woman become pregnant or suspect she is pregnant while she or her partner is participating in this study, she should inform her treating physician immediately. Men treated or enrolled on this protocol must also agree to use adequate contraception prior to the study, for the duration of study participation, and 4 months after completion of obinutuzumab administration.

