5.3 Treatment Regimen

Obinutuzumab or placebo will be administered at a dose of 1000 mg, intravenously, at 3, 6, 9 and 12 months from transplantation. The first dose is administered at day +90 (+/- 10 days), followed by doses at days +180 (+/- 10 days), 270 (+/- 10 days) and +365 (+/- 10 days).

Premedication with histamine blockers and acetaminophen will be provided (see Section 5.5 below), but corticosteroids at the time of obinutuzumab infusion are not permitted. Placebo will be administered with the same premedications and precautions.

No dose modifications are permitted, although doses may be skipped based on unresolved toxicity (see Section 6: Dosing Delays/Dose Modifications). If a dose is missed, the investigator may choose to continue with protocol-specified treatments within the next dosing time period.

5.4 Pre-Treatment Criteria for Doses 1, 2, 3 and 4

There are no criteria for treatment at dose 1. Dose 1 will be administered at the discretion of the provider.

Criteria for treatment at doses 2, 3 and 4 are:

 $\begin{array}{lll} - & WBC & & \geq 2,500/\mu L \\ - & Absolute \ Neutrophil \ Count & \geq 1,000/\mu L \\ - & Platelets & \geq 50,000/\mu L \end{array}$

The occurrence of acute GVHD prior to doses 2, 3, 4 is allowed as long as all GVHD symptoms are resolved to Gr 0 for hepatic and gastrointestinal disease and Gr I for cutaneous disease, per section 3.2.43.2.4

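### The partner-pregnancy report to the drug supplier stops at three months after therapy, before the contraception period that the protocol sets for men has ended

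*Combined protocol and SAP*

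**What the plan says.** **Contraception (section 3.1.11).** The section states that fetal effects of obinutuzumab are not known. Its general sentence says that "women of child-bearing potential and men must agree to use adequate contraception", and the period is "prior to study entry and for the duration of study participation". A further sentence, for men only, sets the period as "for the duration of study participation, and 4 months after completion of obinutuzumab administration". Women have no corresponding period counted from the last dose. The section also asks a woman who is or may be pregnant, while she or her partner is on study, to tell her treating physician at once.

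**Reporting (section 7.4.4).** A report goes to Roche/Genentech, and the outcome is followed, when a female patient "becomes pregnant while receiving obinutuzumab or within one year after the last dose of obinutuzumab", or when "the partner of a male patient becomes pregnant while receiving therapy or within three months of completing therapy".

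**Timing.** Section 5.3 places the fourth and last dose at day +365, with a window of 10 days either side. Section 5.10 states: "Research subjects will be followed until 2 years from the time of transplantation, or until death, whichever occurs first". Under the same section, follow-up of a person who withdraws consent ends at withdrawal.

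**The concern.** Both male periods have a limit counted from the end of treatment, and the limits differ: 4 months for contraception and 3 months for reporting. The longer one marks the time during which the protocol wants conception avoided. A conception in that time is the event that the safety system would want to know about, yet the duty to send it to the supplier and obtain the outcome has already ended.

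Events will be few, so each report carries weight. The stake is completeness of safety capture. Sample size, power and type I error are not involved.

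**Working it through.** No figure in the plan needs reproducing. The check compares the stated periods and uses calendar arithmetic, with 3 months taken as about 91 days and 4 months as about 122 days.

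**Men, post-treatment figures only**
- Contraception: 4 months after completing obinutuzumab (3.1.11).
- Reporting: 3 months after completing therapy (7.4.4).
- Interval without a reporting duty under 7.4.4: 4 − 3 = 1 month. After a day-365 dose this is day 365 + 91 = 456 to day 365 + 122 = 487.

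**Men, if study participation means follow-up to 2 years (an assumption)**
- Contraception runs to about day 2 × 365 = 730 (5.10).
- Reporting ends at about day 456.
- Interval: 730 − 456 = 274 days, about 9 months.
- With the 10-day dosing window, reporting ends between day 446 and day 466, so the interval is 264 to 284 days.

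**Does another section close the male interval?**
- 3.1.11: the treating physician is told during participation. No duty to report onward or to obtain the outcome follows from this.
- 7.3.1: serious adverse events go to the Overall PI until 30 days after the last dose, which is shorter than three months.
- 7.4.4, birth-defect sentence, and 7.4.6, post-study congenital anomaly: both concern offspring of female patients.
- 7.4.6, other post-study events: these must be serious and attributed to earlier obinutuzumab exposure. A continuing partner pregnancy without a complication does not meet that by itself.
- 7.6: pregnancy reports are mentioned, but no different window for partners is given.

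None of these sets a general duty to report a partner pregnancy to the supplier after month 3.

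**Women who complete dosing and follow-up**
- Contraception, on the same reading of participation: to about day 730.
- Reporting: day 355 + 365 = 720 to day 375 + 365 = 740.
- The two ends agree within about 10 days.

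**Women who leave the study itself**
- Assumed example: dose 1 only, at day 90, and consent withdrawn at day 120.
- Contraception requirement ends at day 120. Reporting runs to day 90 + 365 = 455.
- Days inside the reporting window with no contraception requirement: 455 − 120 = 335.

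**The case against.** The strongest reply is that contraception is an eligibility undertaking and pregnancy reporting is a safety-reporting duty. A site can comply with both, and no section says that the periods must match. That is correct: no one is given incompatible instructions. What stands is narrower. As written, the reporting duty for partners ends while the protocol's own precaution for men is still running, and no reason is given.

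A second reply is that 9 months is too large. It depends on what study participation means, and the documents do not call the whole of participation a period of fetal risk. This also stands. The only period that 3.1.11 counts from dosing is 4 months, so 1 month is the firm figure and 9 months is conditional. Randomisation is 1:1 against placebo, so only about half of the men will have received obinutuzumab.

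Third, 7.4.4 classes any abortion as a serious event to be reported quickly, and that sentence has no window of its own. It may catch some partner pregnancies after month 3, but not one that continues.

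Fourth, the consent pages were not available for this review and may hold contraception instructions for women. The point about women is therefore limited to the protocol text.

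**Conclusion.** The mismatch for men is real and can be seen by setting 3.1.11 beside 7.4.4. It covers 1 month on the post-treatment figures, and about 9 months after a month-12 dose on the assumption that participation means follow-up to 2 years. The point about women is secondary. It applies to those who leave the study itself, for example by withdrawing consent. Women who only stop treatment remain in follow-up under 5.10.

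A reader might infer more than the documents support:
- **That these partner pregnancies would go wholly unreported.** While the man is on study, 3.1.11 has the treating physician told. What is missing is the duty to report to the supplier and follow the outcome.
- **That women who leave early have no stated period at all.** Their reporting period is stated in 7.4.4 as "within one year after the last dose of obinutuzumab", and it is not limited to women still on study. Only a contraception period after the last dose is missing.
- **That 7.4.4 supplies the trial's only fetal safety data.** Sections 7.4 and 7.4.6 separately cover congenital anomalies in the offspring of female participants, and 7.6 covers product use during pregnancy or breastfeeding.

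Expected events are few. The matter is minor but cheap to settle.

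**What to change.** The sponsor and the drug supplier should reconcile 3.1.11 with 7.4.4 so that partner-pregnancy reporting and outcome follow-up do not end before the contraception period that the protocol itself sets for men. They should also state what study participation means in 3.1.11, and clarify the contraception period for women who leave the study early. They set the lengths. This review does not say which existing figure is right, how a period should be counted, or that one period must serve both purposes.

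The cost is an edit to the protocol and the consent form and possibly a few more pregnancy reports. Visits, sample size and the efficacy analysis do not change.
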